## 9. STATISTICAL CONSIDERATIONS

### 9.1. Statistical Hypotheses

The primary null hypothesis is that there is no difference in survival between ravulizumab + BSC and BSC alone as measured by the difference in the proportions surviving at Day 29 between the 2 treatment groups. The alternative hypothesis is that ravulizumab + BSC will improve survival at Day 29 compared with BSC alone.

The null hypotheses associated with the secondary objectives are that ravulizumab + BSC is no different than BSC alone for the respective endpoints; the alternative hypotheses are described below:

1. Number of days free of mechanical ventilation: The alternative hypothesis is that treatment with ravulizumab + BSC will increase the number days free of mechanical ventilation at Day 29 compared with BSC alone.
2. Duration of ICU stay: The alternative hypothesis is that treatment with ravulizumab + BSC will reduce the number days in the ICU at Day 29 compared with BSC alone.
3. Change in SOFA score: The alternative hypothesis is that treatment with ravulizumab + BSC will improve changes in SOFA score at Day 29 compared with BSC alone.
4. Change in SpO2/FiO2: The alternative hypothesis is that treatment with ravulizumab + BSC will improve changes in SpO2/FiO2 at Day 29 compared with BSC alone.
5. Duration of hospitalization: The alternative hypothesis is that treatment with ravulizumab + BSC will reduce the number days in the hospital at Day 29 compared with BSC alone.
6. Survival (based on all-cause mortality) at Day 60 and Day 90: The alternative hypothesis is that ravulizumab + BSC will improve survival at Day 60 and Day 90 compared with BSC alone.

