### 9.2. Sample Size Determination

A sample size of 243 patients (162 ravulizumab + BSC, 81 BSC alone) is required to ensure at least 90% power and detect an improvement in survival from 60% in the BSC alone group to 80% in the ravulizumab + BSC group at Day 29.

This sample size calculation assumes:

- 1-sided Z-test of the difference in 2 proportions,
- Type I error = 0.025,
- Pooled variance,
- 2:1 randomization on the 2 treatment groups,

- One interim analysis at 50% information which will be after collecting primary efficacy data on approximately 122 patients. The early stopping boundaries for efficacy and futility (nonbinding) will be constructed using  $\alpha$ -spending function as Lan-DeMets spending function with O’Brien-Fleming flavor and  $\beta$ -spending function as Gamma(-4) (Lan, 1983; Hwang, 1990).

Considering a nonevaluable rate of 10%, this study is planned to randomize approximately 270 patients (180 ravulizumab + BSC, 90 BSC alone).

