5.1.2.3. Duration of ICU Stay

The duration of ICU stay is defined as the total number of days from Day 1 to Day 29 that the patient is in the ICU.

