5.1.2.5. Duration of Hospitalization

The duration of hospitalization is defined as the total number of days from Day 1 to Day 29 that the patient is in the hospital.

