- Worst-case scenario: missing days up to Day 29 for patients randomized to ravulizumab + BSC group will be considered as alive and not free of mechanical ventilation and missing days for patients randomized to BSC group will be considered as alive and free of mechanical ventilation for the remaining days up to Day 29
- All available data: no imputation of missing data
- Best-case scenario: missing days up to Day 29 for patients randomized to ravulizumab + BSC group will be considered as alive and free of mechanical ventilation and missing days for patients randomized to BSC group will be considered as alive and not free of mechanical ventilation for the remaining days up to Day 29
- Delta-adjustment tipping point analysis ([O’Kelly and Ratitch, 2014](#)): missing data for patients randomized to ravulizumab + BSC group are imputed by shifting the number of days alive and free for the observed patients downward by delta until any positive conclusion drawn from the primary analysis is reversed; refer to [Appendix 9.5.2.2.1](#) for additional details

7.2.2.2. Duration of ICU Stay at Day 29

The duration of ICU Stay at Day 29 will be summarized by treatment group for all patients and by mortality. Duration of ICU stay at Day 29 will be compared between the 2 treatment groups using an ANCOVA, adjusting for age and randomization stratification factor, among survivors (ie, the number of days alive and not in the ICU). Missing data will be handled as described for number of days free of mechanical ventilation at Day 29. The proportion of patients discharged

from the ICU will also be summarized and compared between the 2 treatment groups in a similar manner as the primary analysis of the primary endpoint.

7.2.2.3. Change from Baseline in SOFA Score at Day 29

Changes in SOFA score from Day 1 to Day 29 will be summarized by treatment group and study visit for all patients and by mortality.

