9.4.5. Definition of Durations

9.4.5.1. Number of Days Free of Mechanical Ventilation at Day 29

The number of days free of mechanical ventilation at Day 29 among survivors (ie, the number of days alive and free of mechanical ventilation) will be defined as:

Number of days alive – Number of days on mechanical ventilation, where

- Number of days alive = Earliest of Day 29 Visit Date or Disposition Date (for death) – Date of Day 1 + 1; set to 29 if > 29.

- Number of days on mechanical ventilation = sum of total number of days with mechanical ventilation from Date of Day 1 to Date of Day 29 Visit or Disposition Date (for death) ; set to 29 if > 29.

9.4.5.2. Duration of ICU Stay at Day 29

The duration of ICU stay at Day 29 among survivors (ie, the number of days alive and not in the ICU) will be defined as:

Number of days alive – Number of days in ICU, where

- Number of days alive is as defined in [Section 9.4.5.1](#).
- Number of days in ICU = sum of total number of days in ICU from Date of Day 1 to Earliest of Date of Day 29 Visit or Disposition Date (for death); set to 29 if > 29.

Number of days from first ICU date to Day 1 = Date of Day 1 – Date of first ICU entry; set to zero if negative.

9.4.5.3. Duration of Hospitalization at Day 29

The duration of hospitalization at Day 29 among survivors (ie, the number of days alive and not hospitalized) will be defined as:

Number of days alive – Number of days in hospital, where

- Number of days alive is as defined in [Section 9.4.5.1](#).
- Number of days in hospital = sum of total number of days in hospital from Date of Day 1 to Earliest of Date of Day 29 Visit or Disposition Date (for death); set to 29 if > 29.

Number of days from hospitalization to first dose date = Date of Day 1 – Date of hospitalization.

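### Ranks 2 and 5 are hypothesised, named and defined as days in the ICU or hospital but tested as days alive and not there, so a significant result does not by itself support a shorter-stay claim

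*SAP*

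**What the plan says.** **Hypotheses.** Protocol 9.1 states that ravulizumab "will reduce the number days in the ICU at Day 29 compared with BSC alone" (item 2) and "will reduce the number days in the hospital at Day 29 compared with BSC alone" (item 5).

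**Definitions.** SAP 5.1.2.3 has duration of ICU stay "defined as the total number of days from Day 1 to Day 29 that the patient is in the ICU". SAP 5.1.2.5 defines duration of hospitalization as "the total number of days from Day 1 to Day 29 that the patient is in the hospital".

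**Names.** The closed testing order (Protocol 9.4.1.3, SAP 7.2.2) lists rank 2 as duration of ICU stay and rank 5 as duration of hospitalization.

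**Tested variable.** SAP 7.2.2.2 and 7.2.2.5 compare days alive and not in the ICU, and days alive and not hospitalized. In SAP 9.4.5.2 the wording attached to the ICU endpoint is "ie, the number of days alive and not in the ICU) will be defined as", followed by days alive minus days in the ICU; 9.4.5.3 is parallel for hospital. Days alive run to the Day 29 visit or to death.

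**Disclosure.** SAP 4.1 presents the change as a clarification, calls it a composite strategy for death, and says that the SAP's analyses take precedence over the protocol. The words *among survivors* still stand in 7.2.2.2, 9.4.5.2 and 9.4.5.3, and in the matching ventilation text (7.2.2.1, 9.4.5.1).

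**The concern.** In the hypotheses, names and Section 5 definitions a higher value is worse; in the variable tested it is better. The same SAP uses one name for two opposite quantities. This is more than labelling, because the two can move in different directions. A patient who dies early in the ICU has a short ICU stay but no ICU-free days. Saving that patient tends to add ICU days and ICU-free days together.

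Ranks 2 and 5 are tested only after the survival test has succeeded, which is when the days-alive part of the composite favours ravulizumab. A significant result set against the hypothesis as written would read as a shorter stay, and that statement could be wrong in direction.

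**Working it through.** **1. The plan's own figure.** The documents give no power for ranks 2 and 5. The survival inputs come from the primary sample size (Protocol 9.2): 60% v 80%, 2:1, "1-sided Z-test of the difference in 2 proportions", "Type I error = 0.025", pooled variance. The pooled proportion is (2 × 0.8 + 0.6)/3 = 0.733. The BSC arm needs [1.96 × √(0.733 × 0.267 × 1.5) + 1.282 × √(0.24 + 0.16/2)]² / 0.2² ≈ 80, so 240 in total before the interim look. The stated 243 (162 and 81) gives 90.4% power in the fixed design, and 243/0.9 = 270. The inputs reproduce.

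**2. The identity.** For each patient the tested value is days alive minus days there. So:

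difference in tested variable = difference in mean days alive − difference in mean days there.

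Its null is equal mean days alive and out of the ICU or hospital. That is not the null of equal days there.

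**3. Expected values.** Assumptions not in the documents: survivors stay S days in both arms, and deaths occur in the ICU or hospital at mean Day d, with all days until death spent there. With survival 0.8 v 0.6:

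- Days alive: difference 0.2 × (29 − d).
- Days there: 0.8S + 0.2d v 0.6S + 0.4d, difference 0.2 × (S − d).
- Tested variable: 0.8 × (29 − S) v 0.6 × (29 − S), difference 0.2 × (29 − S).

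The tested difference is positive for any S below 29. Days there are longer on ravulizumab whenever S exceeds d.

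**4. How often the test favours ravulizumab.** Simulated at 180 v 90 patients, two-sided 0.05, 2000 to 3000 trials per scenario. Survivors' stays had SD 7.5 to 8 days (ICU) or 6 days (hospital). Age and stratum were unrelated to outcome, so covariate adjustment matters little. Values are ravulizumab v BSC.

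| Setting | S | d | Mean days there | Tested variable | Test favours ravulizumab |
|---|---|---|---|---|---|
| ICU | 12 | 12 | 12.0 v 12.0 | 13.6 v 10.2 (+3.4) | 73% to 76% |
| ICU | 15 | 12 | 14.4 v 13.8 | 11.2 v 8.4 (+2.8) | 68% |
| ICU | 16 | 12 | 15.2 v 14.4 | 10.4 v 7.8 (+2.6) | 62% |
| ICU | 20 | 12 | 18.4 v 16.8 | 7.2 v 5.4 (+1.8) | 42% |
| ICU | 20 | 8 | 17.6 v 15.2 | 7.2 v 5.4 (+1.8) | 46% |
| Hospital | 20 | 12 | 18.4 v 16.8 | 7.2 v 5.4 (+1.8) | 59% |
| Hospital | 23 | 12 | 20.8 v 18.6 | 4.8 v 3.6 (+1.2) | 37% |

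A test on days there would declare a shorter stay in about 3% of these trials or fewer. Among trials with a significant primary, with d = 12, the ICU rates for S = 12, 16 and 20 are 78%, 66% and 45%. For S = 16, in 73% of those wins the observed mean ICU days were equal or longer on ravulizumab.

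**5. Where the effect stops.** With no survival difference the favourable rate is 2.0%, so mortality drives the result. If ravulizumab survivors stay four days longer in the ICU (20 v 16, d = 12), the tested variable is 0.8 × 9 = 7.2 v 0.6 × 13 = 7.8 and the rate falls to 0.8%.

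**The case against.** **The change is disclosed and precedence is set.** This stands in part. SAP 4.1 names the composite and the sections it affects, so an analyst knows what to test, and a reader who inferred a concealed switch would be wrong. But the precedence clause places the SAP's analyses above the protocol. It cannot settle SAP 5.1.2.3 and 5.1.2.5 against SAP 9.4.5, and it does not restate the hypotheses. That a shorter stay would be claimed is an inference from the hypotheses as written; no section says so.

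**Among survivors.** Read literally, days alive would be about 29 for everyone analysed, survival could not drive the comparison directly, and the favourable rate would be 2% to 3% when survivor stays are equal. SAP 4.1's composite description and the death date in the 9.4.5 formula support the all-patient reading, but the phrase leaves it unresolved. The literal reading would also select patients on a post-randomization outcome.

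**No table of actual days.** A reader might infer that days in the ICU would never be shown by arm. The text does not establish that. SAP 7.2.2.2 says "The duration of ICU Stay at Day 29 will be summarized by treatment group for all patients and by mortality"; under 5.1.2.3 that is days in the ICU, under 9.4.5.2 it is ICU-free days. Proportions discharged are also compared, and by-patient efficacy listings are planned. The gap is that actual days are not guaranteed. Nor are the economic inputs in Protocol 8.13 reversed, since 9.4.5 still derives days in the ICU and in the hospital separately.

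**Type I error and larger rates.** Setting these rates against a nominal 2.5% might suggest an inflated error rate. It would be wrong to: the composite's own null is false in every table row. A reader might also fix mean days there as equal in both arms and obtain 97% to 99% for hospital. That needs ravulizumab survivors to leave earlier, for example (0.2 × 12 + 0.6 × 20)/0.8 = 18 days v 20, which builds in a real benefit. The table avoids this.

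**Conclusion.** The mismatch is in the text and should be corrected. The composite is a sound choice and its test is valid for what it measures. What fails is the step from a significant rank 2 or 5 result to the hypothesis in Protocol 9.1. On the all-patient reading, survival of 80% v 60% alone makes the test favour ravulizumab in roughly 37% to 76% of trials, while mean days in the ICU or hospital are equal or up to 0.2 × (20 − 8) = 2.4 days longer on ravulizumab.

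The percentages depend on assumed stays, death times and spread, and they are not conditioned on earlier ranks (rank 1 for rank 2; ranks 1 to 4 for rank 5). The identity in step 2 needs none of those assumptions.

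**What to change.** Keep the composite ANCOVA and the rank order, and make these changes:

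1. Rename rank 2 to days alive and not in the ICU through Day 29, and rank 5 to days alive and not hospitalized through Day 29, wherever the SAP lists them.
2. Replace the definitions in SAP 5.1.2.3 and 5.1.2.5 with the 9.4.5 formulas. State in SAP 4.1 that the hypotheses in Protocol 9.1 items 2 and 5 become an increase in those days.
3. Delete *among survivors* from SAP 7.2.2.2, 9.4.5.2 and 9.4.5.3, and from the ventilation text in 7.2.2.1 and 9.4.5.1.
4. Make explicit that the by-arm and by-mortality summaries in 7.2.2.2 and 7.2.2.5 also show actual days in the ICU and in the hospital, descriptively.
5. State that a significant rank 2 or 5 result supports a claim about days alive and out of the ICU or hospital, and not a shorter stay.

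The cost is SAP wording and one extra descriptive table from counts that 9.4.5 already derives. No new data, patients, tests or alpha are needed. The sponsor gives up a shorter-stay claim that the test does not support.

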9.4.6. Visit Window Definitions for SpO₂/FiO₂ and PaO₂/FiO₂ Repeated Measures Analyses

The following study days will be analyzed in a repeated measures analysis for changes in SpO₂/FiO₂ and PaO₂/FiO₂: Days 5, 10, 15, 22, 29. The value for each study day will be taken as the last observed value on or prior to the Date of Visit for each study day. Both SpO₂ or PaO₂ and FiO₂ must be available on the same date.

9.4.7. Adverse Events

The analysis of AEs is described in [Section 7.3.2](#).

Treatment-emergent AEs are events with onset dates on or after Day 1 in the study. If the start date of an AE is partially or completely missing and the end (stop) date and time of the AE does not indicate that it occurred prior to Day 1, then the determination of treatment-emergent status will be based on the following:

- If the start year is after the year of Day 1, then the AE is treatment-emergent; else,
- If the start year is the same as the year of Day 1 and
 - the start month is missing, then the AE is treatment emergent; else if

- the start month is present and is the same or after the month of Day 1, then the AE is treatment-emergent; else,
- If the start date is completely missing, then the AE is treatment-emergent.

All other AEs are considered PTAEs.

Patient percentages will be based on the total number of patients in the particular treatment group.

AEs with missing relationship will be assumed to be related to study treatment. AEs with missing toxicity grade will be summarized as a separate category.

9.4.8. Medication Dates

For medication start dates, if day is missing, the first day of the month will be used. If month is missing, January will be used. For medication end dates, if day is missing, the last day of the month will be used. If month is missing, December will be used. If year is missing for start or end date, the analysis date will be considered missing.

9.4.9. SF-12 Calculations

The SF-12v2® Health Survey with a 1-week recall period will be used in this study. The Optum PRO CoRE Scoring Software 1.5 will be used to derive the 8 domain scores and 2 component summary scores. The algorithms used by the software to score the data are described below (excerpted from the [User's Guide](#)).

9.4.9.1. Data Cleaning and Item Recoding

First, the data are checked for out-of-range values. Out-of-range values are any values that are outside the range of acceptable item response values for the SF-12v2® Health Survey. Out-of-range values will be converted to missing values. Next, four items (GH01, BP02, MH03, VT02) are reversed scored. Reverse scoring of these items is required so that a higher item response value indicates better health for all SF-12v2® Health Survey items and summary measures.

9.4.9.2. Item Recalibration

For 11 of the SF12v2 items, research to date offers good support for the assumption of a linear relationship between the item scores and the underlying health concept defined by their scales. However, empirical work has shown that one item, GH01, requires recalibration to satisfy this important scaling assumption. The recommended scoring for item GH01 is: Excellent = 5.0, Very good = 4.4, Good = 3.4, Fair = 2.0 and Poor = 1.0.

9.4.9.3. Computation of Raw Scores

After recoding and recalibrating the required item values, a raw score is computed for each scale. This score is the simple algebraic sum of the final values for all items in that scale. For single-item scales, the raw score is simply the final item value.

9.4.9.4. Standardization of the SF-12v2 Health Survey Scales

The first step in scoring the component summary measures consists of standardizing each SF-12v2® Health Survey scale using a z-score transformation. The z-score for each scale is computed by subtracting the mean (0-100) score observed in the 1998 general U.S. population from each SF-12v2® Health Survey scale score (0-100) scale and dividing the difference by the corresponding scale standard deviation observed in the 1998 general U.S. population.

9.4.9.5. Aggregation of the Scale Scores

After a z-score has been computed for each SF-12v2® Health Survey scale, the second step involves computation of aggregate scores for the physical and mental summaries using weights (factor score coefficients) from the 1990 general U.S. population. An aggregate physical score is computed by multiplying the z-score of each SF-12v2® Health Survey scale by its associated physical factor score coefficient and summing the eight products. If any of the scale scores are missing, then the aggregate physical score is not computed. An aggregate mental score is computed by multiplying the z-score of each SF-12v2® Health Survey scale by its associated mental factor score coefficient and summing the eight products. If any of the scale scores are missing, then the aggregate mental score is not computed.

9.4.9.6. Transformation of Summary Scores

The third step involves transforming the aggregate physical and mental summary scores to the T-score Based (50, 10) scoring. This is done by multiplying each aggregate summary score obtained from Step 2 by 10 and adding the resulting product to 50.

9.4.9.7. Imputation of Missing Items

The Maximum Data Recovery option will be used for missing data estimation. This results in the application of algorithms that compute a scale score for those respondents who have answered at least one item that represents that construct. For the four multi-item scales (PF, RP, RE, MH), item parameters obtained through IRT methods are used to estimate a missing value on an item based upon a respondent's response to an answered item. Additionally, a PCS and MCS score is calculated for those respondents who have calculated scores on at least seven of the eight SF-12v2® Health Survey scales. However, PCS is not estimated if the PF scale is missing, and MCS is not estimated if the MH scale is missing.

9.4.10. EQ-5D-5L Calculations

The EQ-5D-5L version will be used in this study. EQ-5D health states, defined by the EQ-5D descriptive system, may be converted into a single summary index by applying a formula that attaches values (also called weights) to each of the levels in each dimension. The index can be calculated by deducting the appropriate weights from 1, the value for full health (i.e. state 11111). The collection of index values (weights) for all possible EQ-5D health states is called a value set. EQ-5D-5L index scores for this study will be obtained using the composite time trade-off (cTTO) method based on the Tobit model ([Pickard, 2019](#)). The calculation is illustrated below.

US cTTO		Example: the value for health state 21354
Full health (11111)		Full Health=1
Mobility level 2	-0.096	-0.096
Mobility level 3	-0.122	
Mobility level 4	-0.237	
Mobility level 5	-0.322	
Self-Care level 2	-0.089	0
Self-Care level 3	-0.107	
Self-Care level 4	-0.220	
Self-Care level 5	-0.261	
Usual Activity level 2	-0.068	
Usual Activity level 3	-0.101	-0.101
Usual Activity level 4	-0.255	
Usual Activity level 5	-0.255	
Pain/Discomfort level 2	-0.060	
Pain/Discomfort level 3	-0.098	
Pain/Discomfort level 4	-0.318	
Pain/Discomfort level 5	-0.414	-0.414
Anxiety/Depression level 2	-0.057	
Anxiety/Depression level 3	-0.123	
Anxiety/Depression level 4	-0.299	-0.299
Anxiety/Depression level 5	-0.321	
Health State Index Score		=1-0.096-0-0.101-0.414-0.299=0.090

9.5. Additional details on Statistical Methods

9.5.1. Time to Death, Censoring Time, and Calculations

For the primary analysis, only deaths up to Day 29 will be considered, where time to death \leq 29 days.

For the KM sensitivity analysis of the primary endpoint, a censoring indicator will be equal to 1 if the patient did not die (was censored), and 0 if the patient died on or before 29 days.

For patients who die during the Primary Analysis Period, the time to event (in days) is defined as:

$$\text{Time to Death} = (\text{Date of Death} - \text{Date of Day 1} + 1)$$

For patients who do not die during the Primary Analysis Period, the censoring time (in days) is defined as:

$$\text{Censoring Time} = \min(29 \text{ days}, \text{time on study})$$

where time on study is Disposition Date – Date of Day 1 +1 for patients who have left the study before 29 days or Data Cutoff Date (when the last patient has the Day 29 visit) – Date of Day 1 + 1.

For the secondary endpoint of survival at Day 60 and Day 90, the following will be used:

For patients who die during the Analysis Period, the time to event (in days) is defined as:

$$\text{Time to Death} = (\text{Date of Death} - \text{Date of Day 1} + 1)$$

For patients who do not die during the Analysis Period, the censoring time (in days) is defined as:

$$\text{Censoring Time} = (\text{EOAP Date} - \text{Date of Day 1} + 1)$$

where End of Analysis Period (EOAP) Date is the minimum non-missing value of the following dates: the Data Cutoff Date (when the last patient has the Day 29 visit) and the Final Disposition Date for patients who have left the study before the data cutoff date. Deaths observed after the EOAP date will not be included in the analysis.

These derivations will be repeated with the data cutoff date defined as when the last patient has completed the study.

